## 8. Sharing of Results with Participants

There are no plans to share results with the participants.

## 9. Study Timelines

The study will be closed to enrollment for all patients. Only RCC participants are expected to participate in the study for 2 years. All study related assessments and activities to cease for NSCLC participants. The estimated date for investigators to complete this study is March 1, 2025.

## 10. Inclusion and Exclusion Criteria

### SUBJECT ELIGIBILITY

Eligibility waivers are not permitted. Subjects must meet all of the inclusion and exclusion criteria to be registered to the study. Study treatment may not begin until a subject is registered.

#### 10.1 Inclusion Criteria

- 10.1.1 Age  $\geq$  18 years and  $\leq$  80 years.
- 10.1.2 Pathology-proven or suspected stage 1 or 2 NSCLC and Stage 3 T3N0 RCC, that require surgical resection as the treatment of choice
- 10.1.3 ECOG performance status (PS) 0, 1, or 2.
- 10.1.4 Ability to understand and the willingness to sign an informed written consent.

#### 10.2 Exclusion Criteria

- 10.2.1 Individuals with pure lung ground-glass opacity (GGO) lesions or mixed GGO with <50% solid component.
- 10.2.2 Patients undergoing pneumonectomy
- 10.2.3 History of cancer in the 3 years prior to surgery (except for basal-cell carcinoma of the skin or cervical neoplasia).
- 10.2.4 Contraindication for NSAIDs (peptic ulcer disease, pre-operative chronic kidney disease with eGFR <45 measured with the MDRD equation used widely, including at Emory), allergies or intolerance to NSAIDs, coagulation disorder, or age  $>$  80 years).
- 10.2.5 Having taken an NSAID within 5 days prior to surgery.
- 10.2.6 Immunocompromised status
- 10.2.7 Refusal or inability to understand the protocol and consent form or to receive follow-up in line with the recommendations.
- 10.2.8 Preoperative hemoglobin  $<$  9.0

## 11. Local Number of Participants

Up to 80 patients will be enrolled locally.

## 12. Recruitment Methods

Participants may be identified by review of medical records or physician referral. After an investigator introduces the study to the participant, the consent form may be given in person, mailed, emailed, or sent to the participant through EPIC or the Emory Patient Portal. The study team will follow up with the participant through the methods of communication listed above, by phone, and/or in person to communicate with the participant about the study. The participant will be given time to read the consent form and ask questions. A member of the study team will reach out to the participant to make sure the participant understands all aspects of the study and the participant is ready to sign the consent documentation. The participant may sign the consent forms in a private setting at Emory. Also, the participant has the option to consent by mail. Subjects with LEP may be enrolled and study team members will use Emory IRB approved shortforms to conduct the consent process. Participants will not receive any payment or reimbursement for this study. Study enrolment will cease for NSCLC participates.

### **13. Withdrawal of Participants**

Participation in this study is completely voluntary and participants can withdraw at any time without any consequences. Participants can also be withdrawn from the study without their consent if their safety is at risk. This is unanticipated for this study. The revocation form specifies the procedures for participants withdrawing from the study.

### **14. Risks to Participants**

#### **Expected Adverse Events - Ketorolac**

The expected incidence of postoperative adverse events attributable to a single preoperative ketorolac dose is expected to be very low. Known gastrointestinal side effects of ketorolac include (gastritis, gastroduodenal ulcer), pulmonary side effects (bronchospasm) and renal side effects (kidney failure) and typically arise with long-term use. Ketorolac has been routinely used for postoperative analgesia in each of disease sites being studies. For example, Freedland, et al., in a retrospective review of 198 patients undergoing donor nephrectomy, found no increased risk of complications or worsening of long-term renal function with postoperative ketorolac use. Similar results have been seen after lung and other cancer resections with postoperative use. Non-selective NSAIDs, such as ketorolac, are known to have the potential to affect platelet function. This does not prevent them from being routinely used after numerous surgical procedures including trauma surgery. However, pre-/intra-operative use of ketorolac has not been studied in lung and kidney surgical patients. Therefore, intra- and post-operative and transfusion rates will be monitored as the primary endpoint for this study. Operative blood loss will also be monitored. Subjects will also be monitored for change in decline in eGFR greater than expected for the procedure. For example, for kidney removal, we expect eGFR to decline 50%, and consider this

expected. However, if it declines by more than 75%, we would consider this unexpected, possibly due to ketorolac.

## **15. Potential Benefits to Participants**

There is significant promise in the use of preoperative ketorolac to decrease the inflammatory response after surgical resection of tumors, thereby potentially reducing the risk of distant metastatic tumor spread and improving survival.

## **16. Data Management and Confidentiality**

### **16.1 Data and Safety Monitoring**

The Data and Safety Monitoring Committee (DSMC) of the Winship Cancer Institute will provide oversight for the conduct of this study. The DSMC functions independently within Winship Cancer Institute to conduct internal monitoring functions to ensure that research being conducted by Winship Cancer Institute Investigators produces high-quality scientific data in a manner consistent with good clinical practice (GCP) and appropriate regulations that govern clinical research. Depending on the risk level of the protocol, the DSMC review may occur every 6 months or annually. For studies deemed High Risk, initial study monitoring will occur within 6 months from the date of the first subject accrued, with 2 of the first 5 subjects being reviewed. For studies deemed Moderate Risk, initial study monitoring will occur within 1 year from the date of the first subject accrued, with 2 of the first 5 subjects being reviewed. Subsequent monitoring will occur in routine intervals per the Winship Data and Safety Monitoring Plan (DSMP).

The DSMC will review pertinent aspects of the study to assess subject safety, compliance with the protocol, data collection, and risk-benefit ratio. Specifically, the Winship Cancer Institute Internal Monitors assigned to the DSMC may verify informed consent, eligibility, data entry, accuracy and availability of source documents, AEs/SAEs, and essential regulatory documents. Following the monitoring review, monitors will provide a preliminary report of monitoring findings to the PI and other pertinent individuals involved in the conduct of the study. The PI is required to address and respond to all the deficiencies noted in the preliminary report. Prior to the completion of the final summary report, monitors will discuss the preliminary report responses with the PI and other team members (when appropriate). A final monitoring summary report will then be prepared by the monitor. Final DSMC review will include the final monitoring summary report with corresponding PI response, submitted CAPA (when

applicable), PI Summary statement, and available aggregate toxicity and safety data.

The DSMC will render a recommendation and rating based on the overall trial conduct. The PI is responsible for ensuring that instances of egregious data insufficiencies are reported to the IRB. Continuing Review submissions will include the DSMC recommendation letter. Should any revisions be made to the protocol-specific monitoring plan after initial DSMC approval, the PI will be responsible for notifying the DSMC of such changes. The Committee reserves the right to conduct additional audits if necessary.

There is no dose escalation planned for this study. The procedures to assure data integrity and protocol adherence are standard of care procedures for this study. Regular data verification and protocol adherence will take place in real time. The standard of care labs will be collected and the PI will review and analyze the results in real time. All data will be recorded and all adverse events will be graded and reported in real time using the CTCAE criteria for evaluation. The oversight of the study team be carried out by the PI reviewing data in real time and results being discussed at the GU working group meetings as necessary. The evaluation of kidney function and labs is standard of care. The study team will not need to be trained on study procedures because there are no new procedures being done that are not part of the standard of care.

## 16.2 Statistical Consideration

### 16.2.1 Sample size determination

It is a pilot study that aims to monitor the hemorrhage side effects who received Ketorolac pre-operatively with the primary safety endpoint being pre-discharge blood transfusion. According to the historical data, among 3280 nephrectomy cases during 2015-2020 in Emory, 20% need a blood transfusion before the discharge, and the mean number of units transfused is 0.286 (standard deviation = 0.12). Among 1212 thoracotomy cases during 2014 -2020 in Emory, 3.4% need a blood transfusion before the discharge, and the mean number of units transfused is 0.098 (standard deviation = 0.075). We anticipate a similar safety profile among the patients who received the pre-operative Ketorolac in this study. A sample size of 50 (25 patients in each disease site) produces a one-sided 90% confidence interval with an upper limit of 0.12 (the distance from the mean number of units transfused to the upper limit = 0.02) for thoracotomy. For nephrectomy, the upper limit of a one-sided 90% confidence interval would be 0.318 (the distance from the mean number of units transfused to the upper limit = 0.032). To account for a possible 10% drop off, we will plan to enroll 28 patients in each disease type.

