## 1. Study Summary

Study Title	A Pilot Study of Biomarker Evaluation and Safety of Pre-Incisional Ketorolac for Patients Undergoing Surgical Resection for Non-Small Cell Lung Cancer and Renal Cell Carcinoma
Study Design	
PATIENT REGISTRATION/RANDOMIZATION
 
Patients will be screened and recruited during the pre-operative period by the responsible medical and surgical team. Blood will be drawn pre-operatively and then at the end of the surgical procedure. Patients who are eligible to be included will be fully informed, consented for additional blood draws and will have the opportunity to ask any questions they may have.
 
Patients will be randomized to either pre-operative Ketorolac group or a concurrent control group who will not receive pre-incisional ketorolac. The concurrent control group is to obtain untreated biologic samples for biologic correlative studies and secondary endpoints. These patients will not be compared to the investigational cohort in regards to the primary endpoint of safety. Patients will be randomized on the day of surgery to either the experimental or control arms. A total of 56 patients will be enrolled into the experimental arm (28 per disease site). About 10 patients will be allocated randomly into the concurrent control group for each disease site separately, for a total of 76 patients enrolled. The enrolment for NSCLC will cease at total of 28 patients consented with total study enrolment goal of 79 Up to 80 patients may be consented on study to account for screen fails and/or withdrawals.

Primary Objective	To test the safety of a single pre-incisional dose of 30 mg ketorolac in patients undergoing surgery for stage I/II NSCLC and stage III RCC, as these are the stages of cancer most likely to develop a recurrence while still noting a benefit from the ketorolac.
Secondary Objective(s)	To evaluate blood and tissue samples pre- and post-operatively to assess the impact of ketorolac on key

	inflammatory biomarkers using a standard cytokine panel.

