#### 16.2.3 Analysis of safety data

All subjects who receive Ketorolac will be included in the summaries and listings of safety data. Overall safety profile will be characterized by type, frequency, severity, timing, during, and relationship of Ketorolac. The rate of pre-discharge blood transfusion and the mean blood unit transfused will be summarize by frequency and proportion with 95% confidence interval for the rate of AEs, and mean (range) and 95% Wald confidence interval.

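### The standard deviations of units transfused behind the sample size are about 4.8 and 7.0 times smaller than the plan's own rates and means allow, so the stated upper limits are too low.

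*Combined protocol and SAP*

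**What the plan says.** Section 16.2.1 names pre-discharge transfusion as the primary safety endpoint and takes its planning values from two historical series at the centre.

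- Nephrectomy, a series of 3,280 patients: "20% need a blood transfusion before the discharge, and the mean number of units transfused is 0.286 (standard deviation = 0.12").
- Thoracotomy, a series of 1,212 patients: "3.4% need a blood transfusion before the discharge, and the mean number of units transfused is 0.098 (standard deviation = 0.075").

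With 25 patients per site, the section says that the design "produces a one-sided 90% confidence interval with an upper limit of 0.12" for thoracotomy, a distance of 0.02 above the mean. For nephrectomy, "the upper limit of a one-sided 90% confidence interval would be 0.318", a distance of 0.032. Enrolment is then raised to 28 per site for 10% drop-off. No other section gives another SD or says that these SDs describe anything other than units transfused.

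Section 16.2.3 plans to report the mean units transfused with "mean (range) and 95% Wald confidence interval".

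**The concern.** A count that is zero for most patients has an SD larger than its mean, because the few transfused patients sit far above the rest. Here both SDs are smaller than their means, although 80% and 96.6% of patients are said to have received nothing. That suggests the SDs are not per-patient values, even though the precision calculation treats them as such.

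This precision statement is the only numerical justification for 25 patients per site. It tells the reader that the mean will be bounded to within 0.02 to 0.032 units. If the SDs are wrong, the study is presented as able to exclude small increases in transfusion that it cannot exclude.

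**Working it through.** **Inputs (all from section 16.2.1).** Nephrectomy: rate p = 0.20, mean m = 0.286, SD 0.12. Thoracotomy: p = 0.034, m = 0.098, SD 0.075. n = 25 per site, one-sided 90%.

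**1. Reproduce the plan's figures.** Distance = t(0.90, 24 df) × SD / √25, with t = 1.318.

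- Nephrectomy: 1.318 × 0.12 / 5 = 0.0316; limit 0.286 + 0.0316 = 0.318, as stated.
- Thoracotomy: 1.318 × 0.075 / 5 = 0.0198; limit 0.098 + 0.0198 = 0.118, stated as 0.12.

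So 0.12 and 0.075 were used as per-patient SDs. The enrolment figure also reproduces: 25 / 0.9 = 27.8, rounded up to 28.

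**2. Smallest SD compatible with p and m.** The variance is smallest when every transfused patient receives the same amount, m/p. Then SD = √(m²/p − m²).

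- Nephrectomy: √(0.4090 − 0.0818) = 0.572; 0.572 / 0.12 = 4.77.
- Thoracotomy: √(0.2825 − 0.0096) = 0.522; 0.522 / 0.075 = 6.96.

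This bound needs no distributional assumption. If units are also assumed to be whole numbers, the minimum mixes the two integers around m/p (1.43 and 2.88). The floors rise to 0.613 and 0.526, which are 5.11 and 7.01 times the stated SDs.

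**3. Limits with the smallest possible SDs, n = 25.**

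- Nephrectomy: 1.318 × 0.572 / 5 = 0.151; limit at least 0.437 (stated 0.318).
- Thoracotomy: 1.318 × 0.522 / 5 = 0.138; limit at least 0.236 (stated 0.12).

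On the 95% Wald scale of section 16.2.3, the half-widths are at least 1.96 × 0.572 / 5 = 0.224 and 1.96 × 0.522 / 5 = 0.205. The stated SDs would give 0.047 and 0.029.

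**4. Other readings of the printed figures.**

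- *Rounding.* With p of 20.5% and 3.45% and m of 0.2855 and 0.0975, the floors fall only to 0.562 and 0.516. Rounding the printed SDs up as well (0.125 and 0.0755) leaves ratios of about 4.5 and 6.8.
- *Mean among transfused patients only.* Both means are below one unit, so they must cover all cases.
- *Variances.* √0.12 = 0.346 and √0.075 = 0.274, still below 0.572 and 0.522.
- *Standard errors of the historical means.* 0.12 × √3280 = 6.87 and 0.075 × √1212 = 2.61. SDs of that size are possible, but dividing the printed figures by √25 would then be wrong, and the true distances would be larger still.
- *Rate and mean from different cases.* With whole units and the mean alone, SD ≥ √(m − m²) = 0.452 and 0.297, or 3.8 and 4.0 times the stated values. The distances are then at least 0.119 and 0.078.

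**5. A check without the historical data.** If one patient of 25 receives one unit and the others none, SD = √(0.96 / 24) = 0.20 and the distance is 1.318 × 0.20 / 5 = 0.053. With whole units this is the smallest non-zero distance possible at n = 25, so neither 0.032 nor 0.02 can be observed.

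**6. How the interval for the mean behaves.** At a 3.4% rate, the chance of no transfusion in 25 thoracotomy patients is 0.966^25 = 0.421. The t and Wald intervals then collapse to zero and miss a mean of 0.098. Coverage therefore cannot exceed 1 − 0.421 = 57.9%, whatever the nominal level.

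**The case against.** The strongest case against is practical. This is a pilot planned on precision, not power. The intervals in section 16.2.3 will use the SDs observed in the trial, so the wrong inputs do not carry into the results. No stopping rule depends on them, and section 9 describes the study as closed to enrolment. All of that is true. It limits the correction to the written rationale and the claimed precision, but that claim still shapes how the safety result will be read.

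Three technical points are fair.

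- The factors 4.8 and 7.0 are 4.77 and 6.96 rounded. With every printed input at its most favourable rounding, they become about 4.5 and 6.8. The conclusion is the same.
- Whole units are an assumption, since the plan does not say how units were counted. The floors of 0.572 and 0.522 do not need it; the mean-only floors and the claim about observable distances do.
- The printed figures could be mislabelled, for example as SDs of yearly averages. That would explain their size, but they would still be the wrong quantity to divide by √25.

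One could also say that the interval's poor coverage and the early closure of the lung cohort are separate from the SD error. They are, and they enter only because a corrected precision statement has to deal with them. Section 16.2.3 already plans a 95% interval for the transfusion rate, but names no method and no planned precision.

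**Conclusion.** The concern holds. The stated SDs cannot be per-patient SDs given the rates and means printed beside them, and the stated limits follow only if they are used that way. The SDs are too small by factors of at least 4.77 (nephrectomy) and 6.96 (thoracotomy) at the printed values. The upper limits are at least 0.437 and 0.236 units, in place of 0.318 and 0.12.

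These figures are planning minima, not forecasts of the observed interval; any variation in units among transfused patients makes them larger. They rest on the rate and mean describing the same cases. Without that, but with whole units, the SDs are still too small by factors of at least 3.8 and 4.0. How the error arose cannot be told from the documents. It should be fixed, but it does not by itself call for a different sample size.

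**What to change.** Keep the sample size and correct section 16.2.1.

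- Recompute the per-patient SDs from the historical cases, then restate the distances and upper limits. If the records are not available, give the minima as floors: SD 0.572, distance 0.151 and limit 0.437 for nephrectomy; 0.522, 0.138 and 0.236 for thoracotomy.
- Add the precision for the proportion transfused, with exact (Clopper-Pearson) limits, because intervals for the mean are unreliable with so many zeros. With 25 patients:
  - 5 transfused: one-sided 90% upper limit 34.0%; two-sided 95% interval 6.8% to 40.7%.
  - 1 transfused: 14.7%; 0.1% to 20.4%.
  - 0 transfused: 8.8%; 0% to 13.7%.
- State the lung precision at the number of ketorolac patients actually reached. Section 1 says "The enrolment for NSCLC will cease at total of 28 patients consented", and as that total covers everyone consented, fewer than 25 may have been treated.

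The cost is a wording change, plus retrieval of per-patient unit counts for the 3,280 and 1,212 historical cases; the documents do not say whether these were kept. No patients are added. The stated precision becomes less favourable.

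### Section 16.2.1 justifies the sample size with a one-sided 90% limit on mean units transfused, an interval that the Section 16.2.3 analysis does not use

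*Combined protocol and SAP*

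**What the plan says.** Section 16.2.1 describes a pilot study "with the primary safety endpoint being pre-discharge blood transfusion". Its historical planning values are, for nephrectomy, 20% transfused, and "the mean number of units transfused is 0.286 (standard deviation = 0.12"; for thoracotomy, 3.4% transfused, and "the mean number of units transfused is 0.098 (standard deviation = 0.075". From these it concludes that 25 patients per site "produces a one-sided 90% confidence interval with an upper limit of 0.12" for thoracotomy (distance from the mean 0.02). For nephrectomy, "the upper limit of a one-sided 90% confidence interval would be 0.318", which lies 0.032 above the mean. Allowing for 10% loss, it enrols 28 per site. It gives no test, power or threshold.

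Section 16.2.3 says how the same quantity will be analysed. Mean units transfused will be given as "mean (range) and 95% Wald confidence interval", and the transfusion rate also gets a 95% interval. Sidedness is not stated. No section plans a one-sided 90% limit, and none explains the change of level.

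**The concern.** In a design sized on precision, the stated width plays the part that power plays elsewhere, and it should describe the interval that will be reported. Here it does not: a one-sided 90% limit is the upper end of a two-sided 80% interval, whereas the analysis uses 95%. The effect is like quoting power at a different alpha from that of the test.

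Section 1 says the controls are not compared with the ketorolac group on the primary safety endpoint, so these two limits are the whole statistical case for 25 per site. Someone who sets the results beside the protocol would find upper limits further from the mean than those stated, with no explanation in the plan.

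**Working it through.** **Inputs** (Section 16.2.1): n = 25 per site, so √n = 5. Nephrectomy: mean 0.286, SD 0.12. Thoracotomy: mean 0.098, SD 0.075. Upper limit = mean + q × SD/√n.

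**1. Reproduce the stated figures.** With the t quantile for one-sided 90% and 24 degrees of freedom, q = 1.318:
- Nephrectomy: 1.318 × 0.12/5 = 0.0316; limit 0.3176. Stated: 0.032 and 0.318.
- Thoracotomy: 1.318 × 0.075/5 = 0.0198; limit 0.1178. Stated: 0.02 and 0.12.

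Both agree after rounding. The loss allowance also agrees: 25/0.90 = 27.8, rounded up to 28.

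**2. Apply the Section 16.2.3 interval to the same inputs.** The standard errors are 0.12/5 = 0.024 and 0.075/5 = 0.015.

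| Reading of the 95% Wald interval | q | Nephrectomy distance; limit | Thoracotomy distance; limit |
|---|---|---|---|
| Two-sided (assumed, by convention) | 1.960 | 0.0470; 0.333 | 0.0294; 0.127 |
| One-sided | 1.645 | 0.0395; 0.325 | 0.0247; 0.123 |

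On the two-sided reading the distance is 0.0470/0.032 = 1.47 and 0.0294/0.02 = 1.47 times the stated one. That ratio sets a normal-based distance against a rounded t-based one; with normal quantiles throughout it is 1.960/1.282 = 1.53. In units, the limits move by 0.333 − 0.318 = 0.015 and 0.127 − 0.12 = 0.007.

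**3. Check whether the SDs can carry a restated limit.** If a proportion p is transfused and the overall mean is m, the patient-level SD is smallest when every transfused patient receives the same amount, m/p. That minimum is m × √(1/p − 1):
- Nephrectomy: 0.286 × √(1/0.20 − 1) = 0.286 × 2 = 0.572, against the stated 0.12.
- Thoracotomy: 0.098 × √(1/0.034 − 1) = 0.098 × 5.33 = 0.522, against the stated 0.075.

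The stated SDs therefore cannot be patient-level SDs if the stated rates and means are right. At these minimum values and n = 25:
- One-sided 90% limits: 0.286 + 1.318 × 0.572/5 = 0.437 and 0.098 + 1.318 × 0.522/5 = 0.236.
- Two-sided 95% Wald limits: 0.286 + 1.96 × 0.572/5 = 0.510 and 0.098 + 1.96 × 0.522/5 = 0.303.

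The SD thus matters far more to the stated limits than the confidence level does. The mismatch of level remains whatever the SD.

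**4. Check n.** Under version 7.0, Section 1 stops the NSCLC group at 28 patients consented in total, while still describing about 10 controls per site. Section 9 says the study will be closed to enrolment for all patients. The documents do not say how many of the 28 received ketorolac, so 25 evaluable ketorolac patients at that site can no longer be assumed.

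**The case against.** The strongest reply is that neither section is false. Section 16.2.1 labels its interval openly as one-sided 90% and computes it correctly, and that limit can be derived from the same mean and standard error that Section 16.2.3 will report. The study is a pilot and the safety analysis is descriptive. The stopping rule in Section 16.2.2 counts transfusions of more than 2 units and does not use these limits. The two-sided reading is inferred, and on the plan's SDs the shift is at most 0.015 units.

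All of this stands, and it limits the size of the point. It does not remove the mismatch: the limit that justifies n is not among the planned results, and a one-sided 95% reading does not give the stated distances either.

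Three stronger readings are tempting, and the documents do not support them:
- *The sample-size arithmetic is wrong.* It reproduces for the interval it names.
- *The trial needs about twice the patients.* Keeping the stated distances with a two-sided 95% interval would take (1.96 × 0.12/0.032)² = (1.96 × 0.075/0.02)² = 54.02, so 55 per site. This is only an illustration: it relies on the doubtful SDs, and the plan sets no precision that must be achieved.
- *The corrected limits are 0.333 and 0.127.* These show the size of the mismatch on the plan's own inputs. They keep SDs that step 3 shows cannot be patient-level.

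**Conclusion.** The point holds as an inconsistency between two sections: the only precision statement behind the sample size is for an interval that the analysis does not plan. On the plan's SDs, with n = 25 and a two-sided 95% interval, the distances are 0.047 rather than 0.032 for nephrectomy and 0.029 rather than 0.02 for thoracotomy, about 47% larger. The mismatch itself rests on the wording of the two sections alone; these sizes rest on the SDs, on n = 25 and on the assumed sidedness. The absolute shift is small and no decision rule is affected, so this is a correction that should be made, not a threat to the trial's conduct or conclusions.

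**What to change.** 1. Use one confidence level and one sidedness in both sections. Either restate the 16.2.1 limits at the two-sided 95% level and say in 16.2.3 that the interval is two-sided, or add the one-sided 90% upper limit by site to 16.2.3. The first needs no new analysis.
2. Before any limit is restated, verify the patient-level SD of units transfused from the historical records and say in 16.2.1 what the SD refers to. Do not simply insert 0.333 and 0.127.
3. Recompute the limits for the number of evaluable ketorolac patients expected at each site under version 7.0, and state that number.

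The cost is a check of the historical data, a few sentences, and a stated precision less favourable than the present one. No change in enrolment is needed.
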